**Hypothesis:**

The primary objective is to describe the PFS in patients undergoing study therapy. This is defined as evidence of disease progression by RECIST, unacceptable toxicity, withdrawal of consent, or discontinuation of the trial for any other reason.

Additional SABR to enlarging lesions will be permitted while on ceritinib, but no change in systemic therapy will be allowed. Patients who demonstrate oligo progression and have disease amenable to repeat courses of radiation therapy may resume ceritinib at the discretion of the treating oncologist until a change in systemic therapy is indicated.

The secondary objective of the study is to report overall survival and in *ALK*-positive lung adenocarcinoma. We will use Kaplan-Meier methods to estimate the overall survival. The rate of overall response and its 95% confidence interval will be estimated using exact binomial method. Response duration will be summarized for patients who responded. Descriptive summary statistics like median, 25% and 75% percentiles will be used.

The secondary objective is also to describe the time to subsequent SABR in patients undergoing study therapy. Patients will be retreated with SABR if feasible. After the initial SABR to persisting lesions, if new lesions appear or if existing lesions enlarge but are amenable to SABR, patients will remain on study and listed as not having progressed. This time to 2nd and 3rd SABR will be recorded and reported. The secondary endpoint will be recorded as time to 2nd and (if applicable) 3rd SABR therapy.

The safety objective of this study to report the toxicity profile of the combination of ceritinib and SABR therapy. Both are well tolerated and routinely used in non-small cell lung cancer.

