### 6.1.5 Duration of Response

Duration of overall response: The duration of overall response is measured from the time measurement criteria are met for CR or PR (whichever is first recorded) until the first date that:

- i. recurrent or progressive disease is objectively documented (taking as reference for progressive disease the smallest measurements recorded since the treatment started) AND is amenable to SABR. This will be defined as time to subsequent SABR.
- ii. recurrent or progressive disease is objectively documented (taking as reference for progressive disease the smallest measurements recorded since the treatment started) and is NOT amenable to SABR. This will be defined as progression on systemic therapy.

The duration of overall CR is measured from the time measurement criteria are first met for CR until the first date that recurrent disease is objectively documented.

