## 9.3 Data Analyses Plans

We will use Kaplan-Meier methods to estimate the progression-free survival, time to 2nd and 3rd SABR and overall survival.

Duration of response (defined in 6.1.5) duration will be summarized for patients who responded. Descriptive summary statistics like median, 25% and 75% percentiles will be used.

Toxicities are dichotomized as none versus any, or none and mild versus moderate to severe.

The rates of overall response, toxicity and adverse events as well as their 95% confidence intervals will be estimated using exact binomial method.

We will compare the rates of toxicity and adverse events in this study with those of historical controls by the Fisher's exact test.

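### Duration of response is given descriptive percentiles and no censoring rule, so incomplete responses must be dropped or counted as finished; it should be estimated by Kaplan-Meier

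*Combined protocol and SAP*

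**What the plan says.** Section 9.3 opens with the time-to-event method: "We will use Kaplan-Meier methods to estimate the progression-free survival", and the same sentence goes on to time to 2nd and 3rd SABR and overall survival. Duration of response is not in that list. The next paragraph gives its method: "Duration of response (defined in 6.1.5) duration will be summarized for patients who responded. Descriptive summary statistics like median, 25% and 75% percentiles". The Hypothesis text in Section 2.0 draws the same contrast. It names Kaplan-Meier for overall survival and then says: "Response duration will be summarized for patients who responded. Descriptive summary statistics like median, 25% and 75% percentiles will be used".

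Section 6.1.5 defines the variable: "The duration of overall response is measured from the time measurement criteria are met for CR or PR". It runs to the first objective documentation of recurrent or progressive disease, whether or not that disease is amenable to SABR. It does not mention death, withdrawal, or a response still ongoing at analysis. Section 9.10.1 has censoring in its heading, but its text says only that missing data are not imputed.

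**The concern.** Duration of response is a time-to-event variable, and some responders will not have a completed value. Sections 4.1.2 and 5.2.3.2 let a patient stop for toxicity, pregnancy, loss to follow-up, patient or physician decision, or death. After voluntary withdrawal no further study data are collected. None of these exits ends a response under 6.1.5. The primary PFS definition in 2.0 and in the 9.1 table does count toxicity, withdrawal and other discontinuation as events, so this gap belongs to duration of response.

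Plain percentiles have no place for an unfinished time. The analyst must drop the patient or enter the unfinished time as if it were finished, and the plan does not say which. Either choice can shorten the reported duration. Under a calendar cut-off the shortfall grows as responses get longer, so it works against the trial's own hypothesis that SABR prolongs control.

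**Working it through.** **Inputs from the documents**
- Accrual 36 months and follow-up 12 months, both cohorts (9.2).
- Median response duration with ceritinib alone: 10 months (ALK-inhibitor naive) and 6.9 months (pretreated); response rate 58% (1.1.2).
- Planned patients: 18 (A) and 15 (B) (9.2). Expected responders: 0.58 × 18 = 10.4 and 0.58 × 15 = 8.7.
- Imaging after every 2 cycles (5.3.1), so the first assessment is at about 2 months.

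**Assumptions not in the documents**
- Exponential response durations.
- Response at month 2.
- Where SABR works, durations double as PFS is planned to: 20 months (A) and 13.8 months (B).
- 10-30% per year leaving without progression (step 3 only).

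**Step 1. Does the sample size rest on 36+12 months?** With uniform accrual, the event probability is p = 1 − (e^(−12λ) − e^(−48λ)) / (36λ), where λ = ln 2 / median. Cohort A has p0 = 0.840 (median 10) and p1 = 0.623 (median 20). Cohort B has p0 = 0.917 (median 7) and p1 = 0.742 (median 14). For a one-sample log-hazard test, n = [(1.645/√p0 + 0.842/√p1) / ln 2]².
- A: n = 17.0, power 0.817 at 18.
- B: n = 15.1, power 0.798 at 15.

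This agrees with the stated 18 and 15. A version using only the alternative variance gives 20.7 and 17.3 and does not agree. On the plan's own alternative, 38% (A) and 26% (B) of patients are still event-free for PFS at month 48.

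**Step 2. Calendar cut-off at 36+12 months.** Follow-up after response is uniform on 12−2 = 10 to 48−2 = 46 months. Let G(t) = 1 for t < 10 and (46−t)/36 from 10 to 46.
- Proportion ongoing = (e^(−10λ) − e^(−46λ)) / (36λ).
- If ongoing times count as finished, quantile q solves e^(−λt) G(t) = 1 − q.
- If ongoing responses are dropped, quantiles come from the density λe^(−λt) G(t), rescaled to 1.

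| True median (months) | Ongoing | Median, counted as finished | Median, dropped | True 75th percentile | 75th percentile, counted as finished |
|---|---|---|---|---|---|
| A doubled, 20 | 40% | 15.4 | 10.2 | 40 | 24.8 |
| B doubled, 13.8 | 28% | 12.4 | 8.9 | 27.6 | 20.6 |
| A historical, 10 | 18% | 10.0 | 7.6 | 20 | 16.9 |
| B historical, 6.9 | 10% | 6.9 | 6.0 | 13.8 | 12.9 |

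Check of the first row at t = 15.35: e^(−λt) = 0.587, G = 30.65/36 = 0.851, product 0.500. The shortfall is 20 − 15.4 = 4.6 months, or 23%. For Cohort B it is 13.8 − 12.4 = 1.4 months, or 10%. When ongoing times are kept, the 25th percentile is correct in all four rows, because it falls before the first censoring time.

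Sensitivity to time to response, 0 to 4 months, with doubled durations and ongoing times kept: the median runs from 16.3 to 14.4 (A) and from 13.2 to 11.7 (B).

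**Step 3. No calendar cut-off.** If the study runs until every patient has progressed or left, incomplete durations come only from those who leave without progression. Let a fraction d leave per year, so c = −ln(1−d)/12 per month. The proportion incomplete is c/(λ+c). The reported median is ln 2/(λ+c). With two constant hazards this is the same whether incomplete times are dropped or counted as finished.

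| True median (months) | Incomplete, d = 10% to 30% | Reported median |
|---|---|---|
| 20 | 20% to 46% | 16.0 to 10.8 |
| 13.8 | 15% to 37% | 11.7 to 8.7 |
| 10 | 11% to 30% | 8.9 to 7.0 |
| 6.9 | 8% to 23% | 6.3 to 5.3 |

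**The case against.** A reader might infer that many responses will be ongoing at the cut-off, so that the reported duration is bound to be understated. The documents do not support that.
- No cut-off is fixed. The 36+12 months is a sample-size assumption. Section 2.3 ends the study only when all 33 patients have progressed, had unacceptable toxicity, withdrawn or discontinued. Section 9.4 is similar, although it waits for 20 and 17 patients where 9.2 plans 18 and 15. Under those rules few or no responses would be ongoing.
- At the historical durations with a 36+12 month cut-off and ongoing times kept, the median is not biased in either cohort.
- The plan does not say that the percentiles are unadjusted. A median and quartiles can be read from a Kaplan-Meier curve.
- Duration of response is not among the primary or secondary endpoints listed in 2.0 or 9.1, and no comparison with published response durations is planned.

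All four points stand as limits on the claim. They do not remove it. Running until everyone progresses or leaves changes the source of the incomplete durations, and step 3 then shows a low median even at the historical durations if 10-30% per year leave without progression. Twice naming Kaplan-Meier for other endpoints and percentiles for this one makes unadjusted percentiles the natural reading. On the kinder reading the censoring rule is still missing.

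**Conclusion.** The point holds as a fault in a supportive analysis. The stated method does not deal with incomplete durations, and nothing else in the plan supplies a rule. Dropping them biases the quantiles downward. Counting them as finished biases those quantiles that lie beyond the earliest censoring times.

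The size depends on the stopping rule, the true duration and the handling chosen. The median can be anywhere from correct (historical durations, 36+12 months, ongoing times kept) to about half its true value (Cohort A with doubled duration and ongoing responses dropped: 10.2 instead of 20). These figures rest on the assumptions listed in the working; the doubling and the 10-30% yearly loss are illustrations, not plan values. The primary PFS analysis is unaffected.

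**What to change.** - In 9.3 and in the Hypothesis text of 2.0, replace the descriptive percentiles with Kaplan-Meier estimates of the median and quartiles with 95% confidence intervals, by cohort, and report the number censored.
- Censor responders without an event at their last adequate tumour assessment. Give the reasons for censoring, because Kaplan-Meier assumes that leaving is unrelated to the course of the response.
- State whether death without documented progression is an event, and align 6.1.5 with that choice.
- State one analysis cut-off that reconciles the 36+12 months in 9.2 with 2.3 and 9.4, including the patient numbers in 9.4.

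The cost is a few sentences in four or five sections and no new data. The downside is precision: with about 9 or 10 responders per cohort, the upper quartile or the upper confidence limit may be not reached, and should be reported as such.

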### 1.3.1.2 Clinical experience

#### 1.3.1.2.1 Clinical safety, efficacy and tolerability

The phase I study of ceritinib demonstrated preliminary evidence of antitumor activity in *ALK*-positive NSCLC. The majority of these patients in this trial had received prior chemotherapy (median of 3 regimens) and the majority also received prior crizotinib. Among 114 response-evaluable patients with at least 18 weeks of follow-up, or who discontinued study earlier, and were treated with ceritinib doses of 400 mg daily or higher, 66 (58%) patients have responded. The response rate to ceritinib is similar regardless of prior *ALK* inhibitor therapy. In patients with NSCLC treated at  $\geq 400$  mg daily, who had previously received crizotinib, the response rate was 57%, and in those who had not previously received crizotinib it was 60%. Post-baseline tumor measurements are available for 104 of the 114 response evaluable patients. A waterfall plot displaying the maximum decrease from baseline in the sum of the longest tumor diameters (Figure 1-1) shows that the large majority of patients treated with ceritinib had a reduction in tumor burden. The median duration of response in patients who responded and were treated at  $\geq 400$  mg daily was 8.2 months (95% CI: 6.9, not estimable), and 71% had a duration of response of 6 months or longer.

After treatment with ceritinib, responses were seen in the CNS in lesions that were not treated with any other modality. The available data from the phase I study indicate that ceritinib has substantial antitumor activity in chemotherapy-treated *ALK*-positive NSCLC patients regardless of prior *ALK* inhibitor therapy.

In the Phase I trial of ceritinib [8], dose-limiting toxicities included diarrhea, vomiting, nausea, dehydration, hypophosphatemia and elevated alanine transferase. The most common adverse events included nausea (82%), diarrhea (75%), vomiting (65%), fatigue (47%), and increased alanine aminotransferase levels (21%). The common grade 3 or 4 adverse events were increased alanine aminotransferase (21%), increased aspartate aminotransferase (11%), diarrhea (7%), and increased lipase levels (7%).

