### 7.1.4 Adverse Reactions

In the dose escalation phase patients were treated on a once daily schedule at the following dose levels: 50 mg, 100 mg, 200 mg, 300 mg, 400 mg, 500 mg, 600 mg, 700 mg and 750 mg. The MTD was determined to be 750 mg daily. Following determination of the MTD in May-2012 the expansion part of the study opened at the 750 mg daily dose level.

During the dose escalation part of the study, first cycle dose-limiting toxicities (DLTs) that contributed to the definition of the MTD included hypophosphatemia (400 mg), ALT elevation (400 mg), nausea with dehydration (600 mg), diarrhea (600 mg and 750 mg), and vomiting (750 mg). There were 3 cases of grade 3 hypophosphatemia, one of which was a DLT that contributed to the MTD determination – this patient was able to continue ceritinib at the same dose. In all cases patients were able to continue therapy without dose modification. Hypophosphatemia was not among the most commonly reported AEs (i.e., < 10%), regardless of relationship to ceritinib treatment.

The majority of adverse events, regardless of relationship to study drug, have been Grade 1-2, and have not required dose interruption or reduction. The most common adverse events were gastrointestinal toxicities, including nausea, diarrhea and vomiting, occurring in 72.7%, 72.7%, and 55.5% of patients, respectively. Other adverse events occurring in more than 20% of patients included fatigue (30.9%), abdominal pain (27.3%), decreased appetite (25.9%), ALT increased (25.0%) and constipation (21.4%). Grade 3 and 4 adverse events were much less common, with none occurring in 16% or more of patients. ALT increase, AST increase and diarrhea were the most common grade 3 or 4 events, occurring in

15.5%, 7.3% and 5.9% of patients, respectively. All other grade 3 or 4 events occurred in less than 5% of patients.

Preliminary ECG data from 220 patients treated at doses of 50-750 mg suggest that ceritinib may have an effect on the QT interval. One patient (700 mg QD dose; <1%) had a QTc > 500 msec and 2 (1.6%) patients (1 at 700 mg QD dose, 1 at 750 mg QD dose) had an increase from baseline QTc > 60 msec.

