#### Severity

Adverse events will be graded by a numerical score according to the defined NCI Common Terminology Criteria for Adverse Events (NCI CTCAE) and version number specified in the protocol. Adverse events not specifically defined in the NCI CTCAE will be scored on the Adverse Event log according to the general guidelines provided by the NCI CTCAE and as outlined below.

- Grade 1: Mild
- Grade 2: Moderate
- Grade 3: Severe or medically significant but not immediately life threatening
- Grade 4: Life threatening consequences
- Grade 5: Death related to the adverse event

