##### **9.10.2.1 Analysis set and grouping for the analyses**

For all safety analyses, the safety set will be used. Toxicities will be dichotomized as none versus any adverse event, or none and mild versus moderate to severe adverse event.

The safety summary tables will include assessments from the on-treatment period, unless otherwise specified.

All safety data collected in the study will be listed regardless of the study period with data collected during the pre-treatment and post-treatment period flagged.

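### Neither toxicity split isolates grade 3 or higher, so the planned historical comparison cannot test severe toxicity like for like

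*Combined protocol and SAP*

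**What the plan says.** Section 9.3 defines two ways of splitting toxicity: "Toxicities are dichotomized as none versus any, or none and mild versus moderate to severe". Section 9.10.2.1 repeats them for the safety analyses: "Toxicities will be dichotomized as none versus any adverse event, or none and mild versus moderate to severe adverse event". The Severity paragraph under Section 7.2.1 gives the scale, with grade 1 as mild, "Grade 2: Moderate", and grade 3 as severe. The second split is therefore grade 0-1 against grade 2 and above.

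Section 9.3 continues: "We will compare the rates of toxicity and adverse events in this study with those of historical controls by the Fisher's exact test". It does not say which split, event terms, control rates, denominators, alpha or sidedness apply. The endpoint table in Section 9.1 makes comparison with historical controls part of the safety endpoint. Section 2.0 (Cohort A) states the hypothesis that the combination is as safe as published experience with the two treatments. Section 9.2 names the published phase I ceritinib trial as the historical control.

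The protocol prints two sets of ceritinib rates:
- Section 1.3.1.2.1, citing the phase I trial. With no grade stated: nausea 82%, diarrhea 75%, vomiting 65%, fatigue 47%, ALT increase 21%. Grade 3-4: ALT 21%, AST 11%, diarrhea 7%, lipase 7%.
- Section 7.1.4. Overall: nausea and diarrhea 72.7% each, vomiting 55.5%, fatigue 30.9%, ALT 25.0%. Grade 3-4: ALT 15.5%, AST 7.3%, diarrhea 5.9%. It adds: "Grade 3 and 4 adverse events were much less common, with none occurring in 16% or more of patients".

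**The concern.** The control information is available at two levels, any grade and grade 3-4. The planned splits use any grade and grade 2 and above. Only the any-grade level appears on both sides. The severe level, where the documents do offer a matching rate, is not among the tested splits. The grade 2+ split has no matching rate in the documents.

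The question at stake is whether adding SABR to ceritinib worsens toxicity. Any-grade gastrointestinal events are already common on ceritinib alone, so harm could appear as higher grades in the same proportion of patients. None versus any cannot register such a shift. A grade 2+ split would register severe cases drawn from patients who would otherwise have had grade 0-1, but not a move from grade 2 to grade 3 or higher.

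**Working it through.** **Matching the levels.** ‘Any grade’ reads the rates printed without a grade as any grade.

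| Split | In the plan? | Historical rate in the documents? |
|---|---|---|
| None vs any | yes | yes |
| Grade 0-1 vs 2+ | yes | none |
| Grade 0-2 vs 3+ | no | yes, as grade 3-4 |

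**Study size.** Sections 9.2 and 2.3 give 18 + 15 = 33, sized for PFS; no power is stated for toxicity. The PFS sizes reproduce closely with a one-sample exponential calculation, n = (z_a/√p0 + z_b/√p1)² / (ln 2)², where p is the event probability under each hypothesis with 36 months' accrual and 12 months' follow-up, z_a = 1.645 and z_b = 0.842.
- Cohort A: p0 = 0.840, p1 = 0.623, n = 17.0 (stated 18).
- Cohort B: p0 = 0.917, p1 = 0.742, n = 15.1 (stated 15).

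**Control size.** Section 1.1.2 gives 246 treated patients, but Section 1.3.1.2.1 gives no denominator with its adverse event rates. I use 246 and, as an assumed lower value, 130.

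**Scenario.** Any-grade diarrhea is unchanged at 75%, and grade 3-4 triples from 7% to 21%. The test is Fisher's exact, two-sided p ≤ 0.05 (assumed), with both cohorts pooled (assumed). The control count is fixed at rate × N. Power is P(X ≥ c), with X binomial(33, true rate) and c the smallest count giving a significant excess.

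| Split | Control N | Control count | c of 33 | True rate | P(significant excess) |
|---|---|---|---|---|---|
| None vs any | 246 | 184 | 30 | 0.75 | 0.021 |
| None vs any | 130 | 98 | 31 | 0.75 | 0.005 |
| Grade 3+ | 246 | 17 | 6 | 0.21 | 0.72 |
| Grade 3+ | 130 | 9 | 7 | 0.21 | 0.56 |

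The 2% is simply the false-positive rate of none versus any in this scenario, because nothing that split measures has changed. For grade 3-4 AST rising from 11% to 33%, a grade 3+ split has power 0.90 (N = 246, c = 8) or 0.81 (N = 130, c = 9).

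**Choice of control set.** Section 7.1.4 gives 220 patients for its ECG data, and its adverse event percentages fit that denominator: 68/220 = 30.9% (fatigue) and 34/220 = 15.5% (grade 3-4 ALT). Two-sided Fisher p-values for illustrative study counts follow. For the Section 1.3.1.2.1 rates, N runs from 114 (that section's response-evaluable number) to 246.

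| Study count | Against Section 7.1.4 | Against Section 1.3.1.2.1 |
|---|---|---|
| Fatigue 17/33 | 68/220: p = 0.03 | 47%: p = 0.70 to 0.71 |
| Grade 3-4 ALT 11/33 | 34/220: p = 0.02 | 21%: p = 0.12 to 0.17 |

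The same study result is significant against one set and not against the other.

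**The case against.** The safety objective is largely descriptive (Sections 2.0 and 9.10.2). Section 9.10.2.2 tabulates treatment-emergent events by CTCAE grade and lists serious events, Section 9.3 gives exact confidence intervals, and Section 11.4 has the monitoring committee review serious events in real time and adverse events quarterly. A reader might infer that a severe excess would go unseen. The documents do not support that: it would be described and monitored, but not formally compared.

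Three other strong readings also fail.
- A reader might infer that the whole test compares unlike quantities, or that none versus any has no room to show an excess. By event term, none versus any matches the any-grade rates, and many of those are far from 100%: fatigue 47% or 30.9%, abdominal pain 27.3%, constipation 21.4%.
- A reader might set a study grade 2+ rate against the 7% or 75% diarrhea rate and conclude that the result is fixed by definition. Section 9.3 specifies no such pairing. What it shows is an unspecified comparator.
- A reader might call the two rate sets an error. They may be different data cuts. The defect is that the plan does not say which is the control.

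The cited publication may also report grade 2 events. That cannot be checked here, so the claim is confined to what the documents print.

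What survives is that the one formal comparison behind the safety hypothesis omits the severe level, where matching rates are printed. Descriptive tables do not carry out that comparison.

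**Conclusion.** The point holds in this limited form. Neither split isolates grade 3 or higher, and the grade 2+ split has no matching historical rate in the documents. The formal comparison therefore cannot test severe toxicity like for like. For a tripling of grade 3-4 diarrhea with the any-grade rate unchanged, the chance of a significant excess is about 2% (0.5%) with none versus any and 72% (56%) with a grade 3+ split, for a control N of 246 (130).

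These figures assume two-sided alpha 0.05, pooled cohorts and a control N in that range; the tripling is illustrative. Tested by cohort, a grade 3+ split would have less power. At N = 246 the threshold is 4 events in either cohort, giving P(X ≥ 4) = 0.54 for 18 patients and 0.39 for 15.

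Separately, the control rates must be settled before any test, since the choice of set alone can change significance.

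**What to change.** In Sections 9.3 and 9.10.2.1:
- Make grade 0-2 versus grade 3 or higher, by adverse event term, the main historical comparison. Say how grade 5 is counted, because the printed rates are grade 3-4.
- Keep any grade (none versus any), by adverse event term, as the second comparison.
- Report the grade 2+ split descriptively with its exact confidence interval, unless a matching published rate is cited.

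In Section 9.3, state which rate set is the control (Section 1.3.1.2.1 or 7.1.4), in one table of term, grade cut, n/N and source, and state alpha and sidedness. Check the ALT increase of 21%, which Section 1.3.1.2.1 gives both overall and for grade 3-4; Section 7.1.4 gives 25.0% and 15.5%.

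The cost is SAP wording, one table, a little more analysis work and one more comparison per event term. CTCAE grades are already collected, so no new data are needed.

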### **1.6 Rationale for dose and regimen selection**

The package insert for ceritinib recommends a starting dose of 750 mg daily. There are recommendations for dose adjustments for toxicity and renal/hepatic impairment. This dose has been associated with gastrointestinal toxicities often necessitating a dose reduction. In clinical practice, the starting dose is lower and side effects mitigated by the addition of food with the dose.

In a phase I study of Ceritinib 450 mg or 600 mg with a low fat meal was compared to 750 mg in *ALK*+ non small cell lung cancer. In this ASCEND-8 study, 137 patients were randomized to 750 mg daily with no food, 600 mg daily with food or 450 mg daily with food. The 750 mg dose patients showed similar

STU042015-076, [name], FormA-ResearchProtocol-V6, Mod\_19, 04-09-20 (1)

CONFIDENTIAL

This material is the property of the [UTSW Simmons Cancer Center](#). Do not disclose or use except as authorized in writing by the study sponsor.

steady state pharmacokinetics, while the 600 mg arm shows a 25% higher PK. The incidences of GI related AE's were lowest in the 450 mg arm with no grade 3 or 4 toxicities, while the remaining toxicities were similar. These data were presented in the Journal of Thoracic Oncology in 2017 (s1184, vol.12, No 1S).

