##### 4.1.1.1 Ceritinib

Patients will self-administer the doses of ceritinib for the cycle.

Ceritinib will be administered orally once daily at a dose of 450 mg ( 3 capsules of 150mg ceritinib) on a continuous dosing schedule. The investigator must instruct the patient to take the ceritinib treatment exactly as prescribed.

- Patients should take ceritinib once daily at approximately the same time each day, in the morning, afternoon, or evening.
- Patients should take ceritinib with food.
- Each dose of ceritinib should be taken with a glass of water and consumed over as short a time as possible (i.e., not slower than 1 capsule every 2 minutes).
- For patients with a gastrostomy tube who are unable to swallow capsules, patient will be instructed on how to prepare mixture. For patients that are unable to swallow capsules, administration can occur through a nasogastric (NG) or gastric (G) tube:
  1. Put on gloves and mask before opening containers. Take the appropriate number of capsules that are needed, out of the containers.
  2. Place a glass bowl in an area with smooth surfaces that is easy to clean.
  3. Carefully open each capsule, one at a time, and pour or tip the contents out of each capsule in the glass bowl.
  4. Carefully check to make sure that both parts of each capsule are empty. Some of the contents may stick to the inside of the capsules. If this happens, use a toothpick (or similar tool) to remove the stuck contents into the glass bowl; work over the bowl.
  5. Fill the glass bowl with at least 40 mL (eight teaspoons) of water. If taking a dose that is 200 mg or less, then use at least 20 mL (four teaspoons of water).
  6. Mix the drug powder with water carefully with the spoon.
  7. Put the end of the syringe in the glass bowl and slowly pull back on the plunger drawing the mixture into the syringe.
  8. Make sure patient is sitting relatively upright, connect the syringe to the patient's NG or G-tube and empty the mixture by slowly pushing the plunger into the syringe until all contents are empty.
  9. Repeat steps 7-8 if necessary, making sure the entire dose is administered.
  10. Once the entire dose is given, rinse the tube by syringing in 20 mL (four teaspoons) twice. If dose is 200 mg or less, then use at least 10 mL (two teaspoons) of water twice for rinsing.
  11. Dispose empty capsule shells, mask and gloves as per the hospital or institutions' guidelines

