## 9.2 Sample Size and Accrual

The results of a Phase I trial of ceritinib in *ALK*-rearranged metastatic adenocarcinoma were reported recently (Shaw et al., 2014). Ceritinib demonstrated activity in patients with an overall response rate of 57% at doses of 400 mg or greater. The PFS reported was 7 months for those with prior crizotinib treatment and 10 months for those who had not received any crizotinib. Toxicities and adverse events were also reported. This study offers contemporary, relevant historical control data for comparison purposes.

The sample size calculation is based on the primary endpoint, progression-free survival, and the assumption that patients are randomized until the end of accrual. The sample size is calculated separately for each cohort.

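### The planned Fisher test compares GI toxicity at 450 mg with food plus SABR with a Phase I trial expanded at 750 mg, so the lower fed dose can offset a GI increase from SABR

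*Combined protocol and SAP*

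**What the plan says.** Section 9.3 commits to a formal test: "We will compare the rates of toxicity and adverse events in this study with those of historical controls by the Fisher's exact test". It fixes the categories as well: "Toxicities are dichotomized as none versus any, or none and mild versus moderate to severe". The objectives table in Section 9.1 sets out to demonstrate the safety of ceritinib followed by SABR, with historical controls as the yardstick. Section 2.0 hypothesises that the combination will be no less safe than published experience with the two treatments.

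Neither 9.1 nor 9.3 says which historical control is meant. Section 9.2 describes the 2014 Phase I ceritinib publication, notes "Toxicities and adverse events were also reported", and continues "This study offers contemporary, relevant historical control data for comparison purposes". Section 9 names no other control.

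On dose, Section 7.1.4 lists escalation levels from 50 to 750 mg and adds "Following determination of the MTD in May-2012 the expansion part of the study opened at the 750 mg daily dose level". In this trial, Section 4.1.1.1 says "Ceritinib will be administered orally once daily at a dose of 450 mg" and tells patients to take it with food. Section 1.6 reports a randomised comparison of 750 mg without food, 600 mg with food and 450 mg with food: "The incidences of GI related AE's were lowest in the 450 mg arm with no grade 3 or 4 toxicities". It describes the remaining toxicities as similar.

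**The concern.** To isolate what SABR adds, the control should match this trial in everything but SABR. The Phase I control also differs in ceritinib dose and food condition. By the account in Section 1.6, that difference lowers GI toxicity here for reasons unrelated to SABR. Section 9 makes no adjustment for it.

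A GI rate at or below the Phase I rate could then be reported as showing no added harm when it partly reflects the lower fed dose. GI toxicity is an adverse event of special interest (Section 7.3.2). The none-versus-any and none/mild-versus-moderate/severe cuts inherit the problem wherever GI events are pooled with others.

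**Working it through.** The plan gives no sample size, significance level, sidedness, margin or power for the safety comparison, so it has no figure to reproduce.

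**Inputs from the documents**
- Trial size: 18 + 15 = 33 (Section 9.2).
- Phase I size: 246 (Section 1.1.2).
- Phase I diarrhea: 75% any grade, 7% grade 3-4 (Section 1.3.1.2.1).
- 450 mg with food: no grade 3-4 toxicities, read as GI (Section 1.6). The study randomised 137 patients to three arms; arm sizes are not given.

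**Assumptions**
- Two-sided 0.05 and both cohorts pooled.
- Phase I counts: 0.07 × 246 = 17.2, taken as 17; 0.75 × 246 = 184.5, taken as 184.
- Comparator arm: 137/3 = 45.7, about 46; range 40 to 50 examined.

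**Step 1. Smallest count flagged as an increase, grade 3-4 diarrhea (Fisher's exact test)**
- Against 17/246: 5/33 gives p = 0.157; 6/33 (18%) gives p = 0.039.
- Against 0/46: 3/33 gives p = 0.069; 4/33 (12%) gives p = 0.027.
- Against 0/40, 4/33 gives p = 0.038; against 0/50, p = 0.022. In both, 3/33 stays above 0.05, so the threshold of 4 does not depend on an equal split.

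At a two-sided 0.1 level, which the plan uses for PFS, the thresholds would be 6/33 and 3/33.

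**Step 2. Chance of a flag if the base at 450 mg with food is 0% and SABR adds d points**

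The chance is P(X ≥ 6) against Phase I and P(X ≥ 4) against the matched arm, with X binomial(33, d).

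| d | Against Phase I | Against 450 mg with food |
|---|---|---|
| 7 | 2.5% | 20% |
| 10 | 11% | 42% |
| 15 | 37% | 75% |
| 20 | 67% | 92% |

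**Step 3. A planned cut: any-grade diarrhea**

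Against 184/246, 29/33 gives p = 0.126 and 30/33 gives p = 0.047, so 30 of 33 patients must be affected. The any-grade rate at 450 mg with food is not in the documents, so I take 45% to 65% as an assumed range and let SABR add 20 points.

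| Assumed base | True rate | Chance of a flag against Phase I | Against 45 patients at the same base |
|---|---|---|---|
| 65% | 85% | 25% | 44% |
| 55% | 75% | 2% | 25% |
| 45% | 65% | 0.1% | 36% |

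The last column is not monotone because Fisher thresholds are discrete. The lower the true base at 450 mg with food, the less the Phase I comparison can detect.

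**The case against.** Several points on the other side have force.

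- **The comparator is inferred.** Section 9.3 says only historical controls, and Section 9.2 is the sample-size section. Section 2.0 refers to both treatments, which implies SABR data that Section 9 never identifies. This stands as a caution. Even so, 9.2 mentions toxicities immediately before calling the Phase I trial relevant control data, and it is the only control available to someone following the plan.
- **Grade 3-4 is not a planned cut.** True: moderate corresponds to grade 2 (Section 7.2.1). Steps 1 and 2 illustrate the mechanism. Step 3 uses a planned cut but needs assumed base rates.
- **The events would not disappear.** A reader might infer that four or five severe GI events would be missed. The documents do not support that. Section 9.3 also gives rates with exact 95% confidence intervals, Section 9.10.2.2 tabulates events by severity and relation to treatment, and the monitoring committee reviews serious events as they are reported (Section 11.4). Only the Fisher flag would be absent.
- **No decision rule equates non-significance with safety.** Correct, and Sections 2.0 and 9.10.2 also speak of reporting or describing toxicity. But 2.0 and 9.1 also say demonstrate, and the Fisher test is the only formal comparison offered for that.
- **GI exposure to SABR is limited.** Section 8.3.3 excludes metastases in the esophagus, stomach, intestines or mesenteric nodes, and Section 8.6.4 sets bowel dose constraints. Liver and adrenal targets remain possible, so some GI exposure can occur; its contribution is not quantified.

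A reader might also infer that the plan leaves two sets of Phase I rates open, since Section 7.1.4 gives lower figures than Section 1.3.1.2.1 (nausea 72.7% against 82%, fatigue 30.9% against 47%), so that the choice of set could reverse a result. The documents largely answer this. Section 9.2 names the 2014 publication, which is reference 8. Section 1.3.1.2.1 attributes its rates to reference 8, and nothing in Section 9 points to 7.1.4.

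**Conclusion.** The concern holds for GI toxicity and for pooled any or moderate-to-severe categories that include it. Following Section 9 as written, the lower fed dose and SABR are confounded in a direction that favours a finding of no added harm, and a GI increase from SABR can go unflagged.

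The direction is clear relative to the 750 mg expansion. The size is not, because the doses behind the rates in Section 1.3.1.2.1 and the GI counts at 450 mg with food are not in the documents. The illustrative gap of 6/33 against 4/33 rests on a two-sided 0.05 level, pooling to 33, 17/246 for Phase I, and zero grade 3-4 events in 40 to 50 patients at 450 mg with food.

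A reader might extend this to all SABR toxicity, pneumonitis included. Section 1.6 gives no basis for that, since it calls the remaining toxicities similar across the dose arms. Nor would a matched control make a non-significant result proof of safety: with 33 patients, an added 10 points of grade 3-4 events would be flagged only 42% of the time.

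**What to change.** Amend Section 9.3 as follows:

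- For GI toxicity, use the published 450 mg with-food arm of the study cited in Section 1.6 as the comparator, and state its size and counts.
- Limit the Phase I comparison, using the reference 8 rates in Section 1.3.1.2.1, to non-GI toxicities.
- Do not base the safety conclusion on pooled any or moderate-to-severe categories against Phase I.
- State that a GI rate at or below the Phase I rate is not evidence that adding SABR is safe.

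This changes SAP wording only; treatment, visits and data collection are unaffected. The downside is a smaller GI comparator, about 46 patients if 137 were split equally, instead of 246, and so wider intervals. The GI counts must come from the published source, since the protocol does not give them.
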